## 9. DATA HANDLING AND RECORD KEEPING

### 9.1 Data collection and extraction

Data will be derived from electronic patient records collected as part of routine clinical patient care on all general adult wards (excluding maternity) between 2013 (beginning of NELA and collection of data of interest) and 2020. Electronic records will include patient demographics, diagnosis and procedure codes held on the Patient Administration System (PAS), vital sign observations from the Vitalpac™ system, routine blood tests from the pathology database, surgery-specific data from TheatreMan™ and additional data from the National Emergency Laparotomy Audit (NELA; which is only available for patients who underwent laparotomy). Linked data sets will provide information on length-of-stay in-hospital mortality, 30-day mortality, 1-year mortality, re-admission to hospital and subsequent abdominal surgery.

### 9.2 Data Management

All data will be pseudonymised at the point of extraction and the national opt-out will be applied. Identifying characteristics (name, address, date of birth) will be replaced by a study identification number (ID) - age will be recorded as it is required for the analysis. The mapping key will only be known to the data manager and kept in a secure location at PHUT. De-identified data will be held in secure clinical data repositories that will only be accessible by relevant members of the research team for the purpose of this study.

## 10. DATA ANALYSIS

### 10.1 Data set

Patient data will include information on age, demographics, diagnosis, co-morbidities, frailty, vital signs and blood tests as potential risk factors associated with mortality. Each patient's National Early Warning Score (NEWS) will be calculated using their vital signs (21), and their Laboratory Decision Tree Early Warning Score (LDTEWS), based on blood test results. The combined LDTEWS:NEWS risk index is a highly accurate predictor of patient deterioration (unintended admission to intensive care and death) within 24 hours (27).

#### Outcomes

The primary outcomes to be assessed will be length-of-stay, in-hospital, short-term (30-day), and long-term (1- year) mortality. This study will also assess long-term complications, such as re-admission to hospital, additional abdominal surgery and the development of new medical conditions. Additionally, it will observe any relationships between these outcomes and patient characteristics.

### 10.2 Data analysis

Extracted data will be cleaned and quality controlled prior to analysis to ensure all relevant patients have been extracted. Given that our analysis will use only routinely collected, clinical data, missing values are unlikely to pose an issue. Initial analysis of 2018 data confirmed that clinical data within 24h of admission was almost fully complete for a remarkable >97% of admissions, meaning there is likely no need to impute data. We will test whether excluding admissions with missing data will introduce bias.

Our analysis can be broken down into the following steps:

- Comparison of the four treatment groups based on demographics, outcomes and medical pathway. This will include calculating mortality and long-term complication rates (Objective 2).
- Construct and compare risk models for each treatment group to predict short-term and long-term risk and to investigate the effect of both patient and hospital-level factors on outcome (Objective 3).

- Identify patients in each group who are abnormal for the group and might have fared better with a different treatment, using clustering algorithms (Objective 4).

After splitting the data set into subsets for each of the four patient groups using diagnosis and procedure codes (see above), mortality and long-term complication rates will be calculated for each group. Longer-term follow-up will include rates of re-admission to hospital, additional theatre visits and development of new medical conditions, within one year of initial admission with an abdominal emergency. Results will provide updated estimates of the average risks of different surgical procedures as well as the risk of not having surgery. Results will be compared with P-POSSUM mortality. Patient groups will further be characterised the using patient factors. Parameters of interest will include but are not limited to age, sex, mortality, long-term complication rates, admission early warning scores (NEWS, LDTEWS and LDTEWS:NEWS), frailty, medical history (previous ICD-10 codes).

Patient group characteristics will be summarised with proportions for nominal and ordinal variables, means and standard deviations for continuous variables having symmetric unimodal distributions, and medians and interquartile ranges for other continuous variables. Clinical outcomes will be reported as proportions with 95% confidence intervals. Statistical tests of differences in proportions (Chi - nominal variables) and means/medians (ANOVA/Kruskal-Wallis) will be performed. Post-hoc pairwise comparisons will be carried out using Scheffe's method for ANOVA and Dunn's test for Kruskal-Wallis results and Bonferroni corrections for Chi results with significance at  $p < 0.05$ .

In the next step, we will identify which patient characteristics affect the outcome for a specific care pathway. Candidate predictor variables of 30-day mortality will be assessed with simple univariable linear regression and check for non-linearity. For each treatment group, we will construct a logistic regression model with the candidate predictor variables and non-linear terms as needed. Logistic regression performance will be tested using "goodness of fit" and discrimination. Goodness of fit, the ability to correctly predict risk, will be evaluated using the Hosmer-Lemeshow statistic (28) and by 10-fold cross-validation. Discrimination, the ability to rank cases in terms of risk, will be assessed using the Area Under the Receiver Operating Characteristic Curve (AUROC) (29). The relative importance of individual parameters will be assessed by the parameters Wald and t-statistics.

The last objective is to determine outlier clusters of patients who might have fared better on a different care pathway. For each treatment group, machine learning classification algorithms will be used to identify homogenous clusters of admissions in terms of their attributes. Each clustering will be reported by its method, number of clusters and intracluster correlation coefficients (ICCs) with 95% confidence intervals and used to extend the logistic regression risk model for the treatment group to see if the model is improved as measured by a likelihood ratio test. Where this is the case the patient subgroups corresponding to the clusters will be analysed in terms of their clinical characteristics.

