### 7.2 Primary and Secondary Endpoints/Outcome Measures

The primary outcomes to be assessed will be length-of-stay, in-hospital, short-term (30-day), and long-term (1- year) mortality.

Secondary outcomes include: long-term complications, such as re-admission to hospital, additional abdominal surgery and the development of new medical conditions as well as the relationships between any of these outcomes and patient characteristics.

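### The one-year rate of new medical conditions is planned for whole treatment groups, but after discharge the listed sources record a new diagnosis only if the patient returns to this hospital

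*Protocol*

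**What the plan says.** Section 7.2 of the protocol names as secondary outcomes "long-term complications, such as re-admission to hospital, additional abdominal surgery and the development of new medical conditions". Section 10.2 gives the window: "Longer-term follow-up will include rates of re-admission to hospital, additional theatre visits and development of new medical conditions, within one year of initial admission". It also gives the unit of calculation: "mortality and long-term complication rates will be calculated for each group". On reporting it states "Clinical outcomes will be reported as proportions with 95% confidence intervals", followed by "Statistical tests of differences in proportions" using Chi-squared, with Bonferroni correction of the post-hoc pairwise results.

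Section 9.1 describes the sources. The records arise from ward care at one hospital: "Electronic records will include patient demographics, diagnosis and procedure codes held on the Patient Administration System (PAS"), together with vital signs, pathology, theatre data and the national laparotomy audit. The administration system is the only source of diagnosis codes named. No general-practice, other-hospital or registry source of diagnoses appears. Besides length of stay, the linked data are said to supply "in-hospital mortality, 30-day mortality, 1-year mortality, re-admission to hospital and subsequent abdominal surgery". New medical conditions are not in that list.

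**The concern.** The protocol promises a rate for which it names no adequate source. A patient who leaves hospital, lives through the year, develops a new disease and is treated elsewhere or in primary care has no code in these data. Divided by the whole group, that patient counts as having no new condition although nothing was observed.

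Two consequences follow. The rate is too low as an estimate of new disease. A group that is re-admitted more often also tends to show more recorded new disease, even when true incidence is equal, so part of one effect (re-admission) is reported again as a second complication. Differences in survival add to this, since a patient who dies early has less time to return. Section 4.2 cites one-year survival of only 30% without laparotomy in an earlier cohort; whether that applies here is unknown.

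The remark in section 10.2 that missing values are unlikely to matter does not answer the point. Its evidence is completeness of data within 24 hours of admission, not ascertainment after discharge.

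**Working it through.** **Group sizes (section 8).** The protocol's own figures reproduce: 901 × 6.5 = 5,856.5 (stated: over 5,800) and 530 × 6.5 = 3,445 (stated: over 3,400). Laparoscopy at 30% gives 1,033 (stated: over 1,000). The remaining 70% are 2,411 laparotomies.

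**Assumptions, not in the protocol.**
- The true one-year risk of a new condition is q = 20% in both groups.
- Baseline re-admission, a, is the rate among patients without a new condition: 25% v 40%, or 30% v 40%.
- Conditions coded in the index stay, and deaths, are left out of this illustration.

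**Recorded rate** = q × P(re-admitted | new condition).
- Independent: P = a.
- New condition triples the odds of re-admission: P = 3a / (1 + 2a).

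**Understatement** = 1 − P.
- Independent: 80%, 70%, 60% and 50% at re-admission of 20%, 30%, 40% and 50%. This is one minus the assumed rate.
- Odds ratio 3: 57%, 44% and 33% at baseline re-admission of 20%, 30% and 40%.

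**Group comparison with no true difference.**
- 25% v 40%, independent: 0.20 × 0.25 = 5.0% v 0.20 × 0.40 = 8.0%.
- 25% v 40%, odds ratio 3: P = 0.75/1.5 = 0.50 and 1.2/1.8 = 0.667, giving 10.0% v 13.3%.
- 30% v 40%, independent: 6.0% v 8.0%.
- 30% v 40%, odds ratio 3: P = 0.90/1.6 = 0.5625 and 0.667, giving 11.3% v 13.3%.

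**Chance of a false finding.** Four groups give six pairs, so α = 0.05/6 = 0.0083 and the critical value is 2.64. Power ≈ Φ((|difference| − 2.64 × SE₀)/SE₁), where SE₀ is the pooled and SE₁ the unpooled standard error. For 5.0% v 8.0% with 1,033 and 2,411 patients, SE₀ = 0.00955 and SE₁ = 0.00875. So (0.0300 − 0.0252)/0.00875 = 0.55, and Φ(0.55) = 71%. Simulation agrees.

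| Baseline re-admission | Independent | Odds ratio 3 |
|---|---|---|
| 25% v 40% | about 71% | about 54% |
| 30% v 40% | about 27% | about 16% |

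The nominal rate per pair is 0.83%. Only the pairwise step is evaluated, not the preceding four-group test.

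**Smaller cohort.** The synopsis plans 2,500 patients, which does not match section 8. With 59% operated and 30% of those laparoscopic (2,500 × 0.59 = 1,475, so about 442 and 1,032), the independent figures fall to about 27% and 8%.

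**Would a re-admitted-only denominator repair it?** Take odds ratio 3 and q = 20% in both groups.
- Baseline 25%: all re-admitted = 0.20 × 0.50 + 0.80 × 0.25 = 0.30, and 0.10/0.30 = 33%.
- Baseline 40%: all re-admitted = 0.20 × 0.667 + 0.80 × 0.40 = 0.453, and 0.133/0.453 = 29%.

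An equal 20% becomes 33% v 29%: overstated, and in the opposite direction to the whole-group comparison.

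**The case against.** The strongest reply is that the protocol neither defines a new medical condition nor writes out a denominator, and that such detail commonly belongs in a statistical analysis plan, which is not shown. That stands as far as it goes: the whole-group denominator is the natural reading of rates for each group reported as proportions, not an explicit statement. But an analysis plan cannot create diagnoses for patients who never return.

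Stronger readings are tempting, and the protocol does not support them.
- A reader might infer that a new condition can be recorded only at a re-admission. The window opens at the initial admission, so a condition coded in the index stay counts without one. The protocol also does not say whether the administration system holds outpatient codes, although it describes ward records.
- A reader might infer that group differences simply mirror re-admission. They mix re-admission, survival and any true difference. The link is weaker where new disease itself brings patients back, which is plausible for conditions serious enough to count as complications.
- A reader might test at an uncorrected 0.05 under independence and obtain about 90% false significance. The plan's pairwise tests are Bonferroni-corrected, and independence is the less favourable of the two cases shown.
- A reader might infer that patients will be told this rate as their risk of new disease. Section 6.1 speaks of risk of death, and the leaflet text in section 12.3 does not name new conditions.

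This is also one of three examples under a secondary outcome, which limits its weight.

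**Conclusion.** The concern holds in limited form. Followed as written, the plan yields the frequency of new conditions coded in one hospital's records, not the development of new conditions. On the whole-group reading it is understated as incidence, and its group differences partly reflect re-admission and survival. The mismatch between sections 7.2 and 10.2 on one side and section 9.1 on the other is in the text and needs no assumption.

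The size does rest on assumptions. With equal true risk of 20%, unequal re-admission alone produces recorded rates of 5% v 8% or 10% v 13%. False pairwise significance then ranges from about 16% to 71% over the scenarios at the section 8 sizes, and is less frequent at 2,500 patients. If re-admission and survival were equal between groups, the spurious difference would vanish, but the understatement would remain.

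**What to change.** In sections 7.2 and 10.2, relabel the outcome as *new condition coded in this hospital's records within one year*. Report it descriptively for each treatment group, beside that group's re-admission and one-year death rates. Leave it out of the Chi-squared comparison as a separate complication, and state that it is not to be read as the incidence of new disease.

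Do not switch the denominator to re-admitted patients as a correction. That selects on a consequence of the outcome and can overstate the risk and reverse the group difference, as shown above.

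The cost is a few sentences of protocol wording and no new data. What is lost is a formal between-group test for this one secondary outcome.

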The NoLap study does not provide information on the performance of laparoscopic (keyhole) procedures compared to laparotomies for abdominal emergencies. PHUT has championed the use of laparoscopy in emergency surgery, with progressive uptake by all consultants from 2014 onwards (11). By 2018, 60% of cases were completed laparoscopically, far higher than the national average of 8% (1). More importantly, this approach has been shown to be safe, with reduced mortality and length of stay (11). For patients unfit or unable to have any surgery, the Department of Interventional Radiology provides an on-call service to drain sepsis and embolise bleeds under local anaesthesia. In this study, information on the outcomes for patients who had an intestinal emergency managed laparoscopically or had an interventional radiology procedure will be collected. The effect of alternative treatments on patient outcomes will be assessed to determine which patient groups would most likely benefit from these interventions. This will benefit patients by providing clinicians with the scientific knowledge needed to develop better care pathways using these less invasive procedures. This will provide clinicians and their patients with the evidence they need to make a better-informed choice between laparotomy, minimally invasive procedures and symptomatic end of life care.

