#### **7.4 Study cohort**

Data will be derived from electronic patient records collected as part of routine clinical patient care on all general adult wards (excluding maternity) between 2013 (beginning of NELA and collection of data of interest) and 2020.

All patients with a condition that would qualify them for emergency abdominal surgery will be identified, using their ICD-10 diagnosis and OPSC-4 procedure codes which are part of the electronic patient record. Once patients have been identified, they will be screened against the inclusion/exclusion criteria (see below). For each patient, this will include only the first intervention within the study period in the analysis. Subsequent admissions with an abdominal condition or subsequent interventions will be classified as complication and therefore considered as an outcome.

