### **8. SAMPLE SIZE**

This study will identify patients diagnosed with an intestinal emergency who may require surgery and observe patient outcomes, and how they correlate with the treatment they received. Trial analysis of all admissions in 2018 identified 901 patients with an abdominal emergency, 59% (530) of which had surgical intervention, either a laparotomy or a laparoscopy. Scaling these numbers to the study period of 6.5 years, we expect to identify a total of over 5,800 patients with an intestinal emergency and over 3,400 patients undergoing surgery. All UK hospitals have to submit data on all their intra-abdominal procedures to the National Emergency Laparotomy Audit (NELA). From previous analysis of PHUT NELA data (11), at least 30% of patients having an operation will have been completed laparoscopically. This is a remarkably large proportion of laparoscopic procedures compared to the UK average (8% according to NELA database) and will provide us over 1,000 laparoscopies in our study data set.

The PHUT data set includes a sufficient number of outcomes for model development (rule of thumb: 10 outcomes per predictor variable (25)). This study will be looking at a patient population with high mortality. Initial analysis of 2018 data identified in-hospital mortality as the rarest outcome with 23 deaths (4.3%) of patients having surgery and 28 deaths (7.6%) of patients not having surgery. Other outcomes occur in greater numbers. Collective numbers for the 6.5 year study period will therefore provide us with enough outcomes for the development of logistic regression models. The data set will be tested for separation and Firth's correction applied if necessary (26). Based on these numbers, we will be able to establish statistically significant correlations from this data set from a single hospital.

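### Medical history comes from earlier codes in records that open in 2013 with the cohort, so look-back grows from zero to about 6.5 years and differs between laparoscopy and open surgery

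*Protocol*

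**What the plan says.** - **Source of history.** Section 10.2 lists "medical history (previous ICD-10 codes" among the parameters used to characterise the treatment groups. It gives no look-back length. Section 10.1 names co-morbidities as potential risk factors for mortality without stating where they come from.
- **Window.** Section 9.1 takes the records "between 2013 (beginning of NELA and collection of data of interest) and 2020", including "diagnosis and procedure codes held on the Patient Administration System (PAS"). No earlier extract is mentioned.
- **Cohort.** Section 7.4 draws patients from the same dates, and for each patient "this will include only the first intervention within the study period in the analysis". No run-in is stated, so cohort entry can begin on the first day of the data. Section 8 gives the period's length: "Scaling these numbers to the study period of 6.5 years".
- **Outcome.** Section 7.2 makes "the development of new medical conditions" a secondary outcome. Section 10.2 counts "development of new medical conditions, within one year of initial admission with an abdominal emergency". Neither section says what makes a condition new.
- **Calendar trend.** Section 4.2 describes laparoscopy "with progressive uptake by all consultants from 2014 onwards", reaching 60% of cases by 2018. Section 10.2 names no calendar-year term.

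**The concern.** When records and cohort open on the same day, a patient admitted early has almost no earlier codes to find, while a patient admitted late has years of them. The same chronic condition is then often missed in the first and usually found in the second. A missed condition does not show up as missing data. It is recorded as no disease.

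This would matter less if admission date were unrelated to treatment. Here it is related, because laparoscopy patients sit later in the window and so have longer look-back. Three parts of the plan are exposed:

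- the description of the groups by medical history;
- any history term in the group-specific risk models, when those models are compared;
- the new-condition outcome, where a long-standing condition first coded after a short look-back would count as new, mostly in the early years when open surgery was more common.

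Section 4.4 expects the findings to support wider use of laparoscopy, so an artefact that separates these two groups deserves attention before extraction.

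**Working it through.** **The protocol's own figures (section 8).** The 2018 counts are 901 patients, 530 of them operated on, and the period is 6.5 years.

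- 901 × 6.5 = 5,856.5, stated as over 5,800.
- 530 × 6.5 = 3,445, stated as over 3,400.
- 0.30 × 3,445 = 1,033.5, stated as over 1,000 laparoscopies (30% is a lower bound).

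All three reproduce. The protocol gives no figure for look-back.

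**Look-back as written.** Look-back = index date − start of data. It runs from 0 to 6.5 years, with a mean of 3.25 if admissions are evenly spread. Counting from the start of 2013 to the start of 2020 gives a maximum of 7 and a mean of 3.5.

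**Look-back by group.** Assumptions, not in the protocol:

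- the 6.5-year window ends at the start of 2020 and admissions are uniform over it;
- the laparoscopy share *s(t)* is flat at 8% to 30% until 2014, rises linearly to the stated 60% at mid-2018, and is flat after that.

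Mean look-back is the average of *t* weighted by *s(t)* for laparoscopy and by 1 − *s(t)* for open surgery.

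| Share before 2014 | Laparoscopy (years) | Open (years) | Gap |
|---|---|---|---|
| 8% | 4.16 | 2.69 | 1.47 |
| 20% | 3.87 | 2.78 | 1.09 |
| 30% | 3.67 | 2.87 | 0.80 |

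**Recorded history.** Further assumptions: true prevalence is 40% in both groups, and an affected patient has *r* earlier coded admissions per year. The chance that the condition is captured is 1 − exp(−*r* × look-back). At *r* = 0.3 this is 14% after half a year and 86% after 6.5 years. Averaged over each group, recorded prevalence for laparoscopy and open surgery is:

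| *r* | Share before 2014 = 8% | Gap (points) | Share before 2014 = 30% | Gap (points) |
|---|---|---|---|---|
| 0.1 | 13.3% vs 8.9% | 4.4 | 11.8% vs 9.5% | 2.3 |
| 0.3 | 27.0% vs 19.6% | 7.4 | 24.5% vs 20.5% | 4.0 |
| 0.5 | 32.9% vs 25.2% | 7.7 | 30.4% vs 26.2% | 4.2 |
| 1.0 | 37.6% vs 31.6% | 6.0 | 35.6% vs 32.3% | 3.3 |

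The gap is about 2 to 8 points although the true difference is zero. With 3,445 operated patients and *r* = 0.3, one two-sided 5% comparison of the two groups, before any Bonferroni correction, would be significant with a probability of about 80% to nearly 100%.

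**What this does to a history term.** Among patients recorded as having no history, the share who truly have the condition is (40 − recorded) / (100 − recorded). At *r* = 0.3:

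- Share before 2014 of 8%: open (40 − 19.6) / 80.4 = 25.4%; laparoscopy (40 − 27.0) / 73.0 = 17.8%.
- Share before 2014 of 30%: open (40 − 20.5) / 79.5 = 24.5%; laparoscopy (40 − 24.5) / 75.5 = 20.5%.

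So the same recorded status means different health in the two models.

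**The case against.** **The window may not limit history.** Section 10.2 does not say that codes before 2013 are excluded, and the patient administration system may hold them. A look-back length and a rule for new conditions are also details that an analysis plan commonly supplies. This is fair as to the definitions. It does not dispose of the extraction: section 9.1 fixes the dates, section 14.1 completes extraction by month 4, and no later plan can recover codes that were not extracted.

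**Most predictors need no look-back.** Age, NEWS, LDTEWS and diagnosis codes recorded at the index admission do not depend on earlier records. This stands, and it narrows the point. Recorded prevalence would fall to zero on the first day only if index-admission codes were ignored, which the protocol does not say. Using them would also shrink the gaps shown above.

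**No adjusted comparison is planned.** A reader might infer that laparoscopic patients will look sicker than they are, so that adjusted comparisons will over-credit laparoscopy. The protocol does not support that as stated. Section 10.2 plans a separate logistic model for each treatment group, and its tests between groups are unadjusted. The bias can enter only when the separate models are compared, and its effect on a mortality estimate cannot be computed from the document.

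**The calendar extremes overstate the size.** Comparing the first day of data with the final year gives a much larger difference than the one between treatment groups, which is the one that matters.

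**Surgery versus no surgery.** The protocol documents no calendar trend for this contrast, so the point does not reach it.

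The statement in section 10.2 that over 97% of admissions have almost complete data is no answer. It concerns clinical data within 24 hours of admission in 2018, not earlier diagnosis codes.

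**Conclusion.** The concern holds in a limited form. Under the dates as written, look-back depends on admission date and therefore differs between laparoscopy and open surgery. It affects the characterisation of those groups by history, any history term when the group models are compared, and the new-condition outcome if new means not previously coded. It does not touch the measurement of mortality or length of stay.

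The mechanism follows from the protocol; the size does not. The 2 to 8 points rest on the assumed prevalence, coding rate and early laparoscopy share, and on history being taken only from earlier codes. For new conditions, the direction follows from the assumed definition, and no size can be given. It should be corrected before extraction, but it does not undermine the primary outcomes.

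**What to change.** 1. **Extend the extract in section 9.1.** Take diagnosis codes from the patient administration system for a fixed period before the first index admission, preferably several years and as far back as the system allows. A short period would equalise the groups but capture little: at *r* = 0.3, one year finds 1 − exp(−0.3) = 26% of affected patients and two years find 45%.
2. **Apply one look-back to everyone.** Use the same period for every patient, together with index-admission codes, both for medical history and for the condition of no previous code behind a new diagnosis. State that definition in section 7.2 or 10.2. With equal look-back, capture no longer depends on index date and the artefact computed above is zero.
3. **Report all-available look-back as a sensitivity analysis.**
4. **If earlier codes cannot be extracted,** use the first year as a run-in and restate section 8: 901 × 5.5 = 4,955.5 patients, 530 × 5.5 = 2,915 operated on, and 0.30 × 2,915 = 874.5 laparoscopies, against the stated figure of over 1,000. Because 30% is a lower bound and the year dropped is one of low laparoscopy use, the real loss of laparoscopies should be smaller.

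The cost is a somewhat larger extract, and older history of late patients is left out of the main analysis. The earlier extract is preferable to the run-in because it loses no patients.

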#### 4.4 Impact of research

This study will provide new information on the outcomes for ALL patients with abdominal emergencies and the treatment they receive. By identifying groups of patients for whom less invasive procedures or end of life care may be more appropriate, it will support the development of new alternative care pathways.

This study will contribute novel information on the outcomes of minimally invasive procedures in abdominal emergencies (laparoscopy and interventional radiology). This information will be highly relevant to acute hospitals providing an emergency general surgery service across the UK. Initial analysis of the national NELA database has shown that currently only 8% of surgeries for abdominal emergencies in the UK are performed laparoscopically. Early data from Portsmouth Hospitals NHS Trust suggests patients may do better with this approach. The findings from this study will provide the necessary evidence to increase the proportion of laparoscopies nationwide and, thus, potentially significantly reduce risk for patients with abdominal emergencies.

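### Outcomes are tested between treatment groups only without adjustment, and no stated step turns the per-group risk models into a comparison at equal case mix

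*Protocol*

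**What the plan says.** Section 10.1 (Outcomes) sets the targets: "The primary outcomes to be assessed will be length-of-stay, in-hospital, short-term (30-day), and long-term" (1-year) mortality. The first analysis step in section 10.2 is "Comparison of the four treatment groups based on demographics, outcomes and medical pathway". Its methods are fixed there: "Clinical outcomes will be reported as proportions with 95% confidence intervals", Chi-squared for proportions, and for other variables "means/medians (ANOVA/Kruskal-Wallis) will be performed". Post-hoc pairwise tests follow (Scheffe, Dunn, or Bonferroni after Chi-squared) at the 5% level.

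Baseline data are rich: "Patient data will include information on age, demographics, diagnosis, co-morbidities, frailty, vital signs and blood tests as potential risk factors associated with mortality" (section 10.1), plus the combined LDTEWS:NEWS index. They are used in the next step: "For each treatment group, we will construct a logistic regression model with the candidate predictor variables and non-linear terms as needed". Section 10.2 says these models will be constructed and compared. The measures it names are Hosmer-Lemeshow, 10-fold cross-validation, AUROC, and Wald and t-statistics. The cluster step extends the same within-group models.

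The intended use goes beyond description. Section 4.2: "The effect of alternative treatments on patient outcomes will be assessed to determine which patient groups would most likely benefit from these interventions". Section 4.4: "The findings from this study will provide the necessary evidence to increase the proportion of laparoscopies nationwide". Section 7.1 expects the analysis to point to lower-risk treatment options for different patient groups.

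**The concern.** Treatment here is chosen on prognosis. Section 4.3 reports that in the cited cohort the non-operated patients were older (78 vs 63.7 years) and had more co-morbidity, and one of the four planned groups is defined by futility of treatment. A crude difference in mortality or length of stay therefore mixes case mix with treatment.

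A model fitted inside one treatment group cannot separate the two, because treatment is constant within it. Such models can be combined into an adjusted contrast, but only if each is applied to the same patients. No such step is stated, and neither is a pooled model, matching or weighting. The named performance measures describe fit, discrimination and predictor importance within a group. They do not compare treatments.

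At stake is what the study can say about laparoscopy against laparotomy, and surgery against no surgery. The only between-group p-values the plan produces are unadjusted. With several thousand patients they can be very small without any treatment effect.

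**Working it through.** **1. The plan's own figures (section 8).**
- 901 × 6.5 = 5,856.5 (stated: over 5,800).
- 530 × 6.5 = 3,445 (stated: over 3,400).
- 0.30 × 3,445 = 1,033.5 laparoscopies (stated: over 1,000).
- 2018 in-hospital deaths: 23/530 = 4.34%. With 901 − 530 = 371 not operated, 28/371 = 7.55% (stated 7.6%).

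All agree within rounding.

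**2. What the planned test gives on the 2018 counts.**
- Risk ratio, no surgery vs surgery: 0.0755/0.0434 = 1.74.
- Chi-squared = N(ad − bc)²/(product of margins) = 901 × (23 × 343 − 507 × 28)²/(530 × 371 × 51 × 850) = 4.20, p = 0.040 (0.057 with continuity correction).
- Same rates over 6.5 years (about 150 and 182 deaths): 4.20 × 6.5 = 27.3, p = 1.7e-7; odds ratio 1.80 (95% CI 1.44 to 2.25).

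Nothing in this calculation says how much of the 1.74 is case mix.

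**3. How large case mix could be: the cited cohort (section 4.3).**
- Observed 30-day mortality 63% vs 13%: ratio 4.85.
- Predicted mortality 30% vs 12% (ratio 2.50) and 40% vs 17% (ratio 2.35).
- Observed/predicted, then the ratio of these: (63/30)/(13/12) = 1.94; (63/40)/(13/17) = 2.06.
- Share of the crude log ratio matched by predicted risk: ln 2.50/ln 4.85 = 58%; ln 2.35/ln 4.85 = 54%.

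This is indicative only. The two scores are surgical risk models, and mortality in that cohort was far above the local figures.

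**4. Laparoscopy vs laparotomy with no treatment effect.** The protocol gives no case-mix difference between these groups, so the gap is an assumption. Inputs: 1,033 vs 2,412 patients, overall in-hospital mortality 4.34%, crude two-proportion test.

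| Gap in expected mortality due to case mix alone | Rejects at 0.05 | Rejects at 0.05/6 (six pairs) |
|---|---|---|
| 1 point | 25% | 8% |
| 2 points | 78% | about 50% |

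**5. Whether adjustment would help.** Simulation with no treatment effect, 3,445 vs 2,411 patients, 300 runs per setting. Assumptions: one severity score, log-odds slope 1 per SD, mortality between about 3.6% and 7%.

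| Severity gap | Chi-squared rejects | Crude odds ratio | Model with treatment and severity rejects | Adjusted odds ratio | Risk ratio, per-group models standardised to all patients |
|---|---|---|---|---|---|
| 0.25 SD | 57% | 1.26 | 5.7% | 1.00 | 1.00 |
| 0.50 SD | 98% | 1.59 | 3.7% | 1.00 | 1.00 |
| 0.75 SD | 100% | 2.03 | 4.7% | 1.00 | 1.01 |

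Under these assumptions all confounding is measured. Either adjusted route then removes the bias, including the one that starts from the models the protocol already plans.

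**The case against.** The strongest reply is that the first step is descriptive. The Synopsis defines the primary endpoint as a risk per treatment group, not a contrast, and Objective 2 asks for average risks and the profile of typical patients. Crude proportions with confidence intervals are the right estimator for that. This stands, and the crude rates should stay.

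A second reply is that claims about treatment choice hang mainly on the regression. Objective 3 and section 7.1 derive pathways from it, and separate models with common covariates are equivalent to one model with every treatment-by-covariate interaction. This stands in part. The covariates are planned for, and only the step that yields a contrast is absent. A statistical analysis plan, not shown here, might supply it. But the protocol does not leave between-group testing open: it names unadjusted tests and a significance level, and no adjusted counterpart.

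The comparison with P-POSSUM mortality does not fill the gap. No method is given, and it sets groups against a benchmark rather than against each other.

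A reader might infer that the protocol makes the Chi-squared tests its primary inference, or that it will report severity as a treatment effect. The document says neither, and section 4.3 itself raises unmeasured confounding as an explanation in the cited cohort.

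**Conclusion.** The point holds in a limited form. Every stated between-group test of a primary outcome is unadjusted, length of stay included, and nothing turns the per-group models into a comparison at equal case mix. Followed as written, the plan produces no adjusted treatment comparison to carry the claims in sections 4.2, 4.4 and 7.1.

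The size of the bias in this cohort cannot be computed from the protocol. The cited cohort's predicted-risk ratios (2.35 to 2.50) exceed the local crude ratio of 1.74, so case mix could account for all of that difference if a similar gap held here. That is an assumption. It would be wrong to conclude that more than half of the local difference is case mix, or that a false laparoscopy finding is likely: the 54-58% share belongs to another population, and the rejection rates run from 8% to 78% depending on an assumed gap and the significance level. This is a cheap improvement that reduces bias, not a fault in reporting crude risks.

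**What to change.** In section 10.2:

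- Keep crude proportions with 95% CIs as description of average risk, and state that the crude tests are not evidence of a treatment effect.
- Base between-group inference on an adjusted comparison for in-hospital, 30-day and 1-year mortality, with a suitable model for length of stay.
- Choose one route in advance. Either standardise the planned per-group models to a common population (average each group's predicted risk over the same patients, then take differences), or fit one pooled model with treatment group, age (non-linear), sex, diagnosis group, co-morbidity, frailty and admission LDTEWS:NEWS, allowing treatment-by-covariate interactions.
- Report standardised risks and risk differences with 95% CIs beside the crude figures.
- Check covariate overlap and limit adjusted contrasts to groups where it is adequate. If overlap is poor, report the end-of-life/futility group descriptively.

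The cost is a rewrite of part of one section and one further analysis step on data already to be extracted. Differences will probably be smaller and less precise. Sparse outcomes limit how many interactions can be fitted: if laparoscopy patients had the overall surgical in-hospital mortality (assumption), 1,033 × 4.34% gives about 45 deaths. Adjustment does not remove unmeasured confounding, which must still be stated with the results.
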